#### **3.2 Eligibility Criteria**

1. Patients must have histologically confirmed glioblastoma that is progressive or recurrent following radiation therapy and temozolomide.
2. Tumor MGMT methylation status must be available. Results of routinely used methods for MGMT methylation testing (e.g. MSPCR or quantitative PCR) are acceptable.
3. Arm 1 patients must have measurable (defined by at least 1 cm x 1 cm) contrast-enhancing disease by MRI imaging within 21 days of starting treatment.
4. Patients must be able to undergo MRI of the brain with gadolinium. Patients must be maintained on a stable or decreasing dose of corticosteroid regimen (no increase for 5 days) prior to this baseline MRI.

5. Arm 1 patients must be in first recurrence of glioblastoma following radiation therapy and temozolomide.  
Arm 2 patients may have an unlimited number of prior therapy regimens but may not have received prior antiangiogenesis therapy except for bevacizumab (patients may not have received afibbercept, ramucirumab, cediranib, cabozantinib, or XL184).
6. Arm 1 patients must have not received bevacizumab previously.  
Arm 2 patients must have progressed/recurred on bevacizumab as the most recent regimen. Patients on Arm 2 should continue on bevacizumab as clinically necessary to control brain edema.
7. Patients must have a tumor tissue form indicating availability of archived tissue from initial resection at diagnosis of glioblastoma completed and signed by a pathologist. See Section [9.5.1](#). Availability of tissue is not a requirement for study participation.
8. Patients must have recovered from severe toxicity of prior therapy. The following intervals from previous treatments are required to be eligible:
  - 12 weeks from the completion of radiation
  - 6 weeks from a nitrosourea chemotherapy
  - 3 weeks from a non-nitrosourea chemotherapy
  - 4 weeks from any investigational (not FDA-approved) agents
  - 2 weeks from administration of a non-cytotoxic, FDA-approved agent (e.g., erlotinib, hydroxychloroquine, etc.)
9. Patients must be 18 years of age or older.
10. Patients must have a Karnofsky Performance Status  $\geq 60\%$  (i.e. the patient must be able to care for himself/herself with occasional help from others).
11. Patients must have the following organ and marrow function:
 

Absolute neutrophil count	$\geq 1,500/\text{mcL}$
Platelets	$\geq 100,000/\text{mcL}$
Hemoglobin	$\geq 9 \text{ g/dL}$
Total bilirubin	$\leq$ institutional upper limit of normal

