## **8.0 RESPONSE ASSESSMENT / SAFETY AND QUALITY ASSURANCE**

### **8.1 Criteria for Response Assessment**

Subjects with measurable disease will be assessed by the RANO (radiographic assessment in neuro-oncology) criteria (Wen 2010). For the purposes of this study, subjects should be re-evaluated at the end of every 2 cycles (approximately every 8 weeks) with a contrast-enhanced cranial MRI scan. The response will be determined as outlined in the RANO criteria below.

*Measurable disease.* Bidimensionally, contrast-enhancing, measurable lesions with clearly defined margins by MRI scan, with a minimal diameter of 1 cm, and visible on 2 axial slices which are at least 5 mm apart with 0 mm skip. Measurement of tumor around a cyst or surgical cavity, if necessary, requires a minimum thickness of 3 mm. If there are too many measurable lesions to measure at each evaluation, the investigator must choose the largest two to be followed before a participant is entered on study. The remaining lesions will be considered non-measurable for the purpose of objective response determination. Unless progression is observed, objective response can only be determined when all measurable and non-measurable lesions are assessed.

Complete Response (requires all of the following):

- a) Complete disappearance of all enhancing measurable and non-measurable disease sustained for at least 4 weeks. In the absence of a confirming scan 4 weeks later, this scan will be considered only stable disease.
- b) No new lesions.
- c) All measurable and non-measurable lesions must be assessed using the same techniques as baseline.
- d) Subjects must be off corticosteroids (or on physiologic replacement doses only).
- e) Stable or improved non-enhancing (T2/FLAIR) lesions.
- f) Stable or improved clinically.

**Note:** Subjects with non-measurable disease cannot have a complete response. The best response possible is stable disease.

Partial Response (requires all of the following):

- a) Greater than or equal to 50% decrease compared to baseline in the sum of products of perpendicular diameters of all measurable enhancing lesions sustained for at least 4 weeks. In the absence of a confirming scan 4 weeks later, this scan will be considered only stable disease.
- b) No progression of non-measurable disease.
- c) No new lesions.
- d) All measurable and non-measurable lesions must be assessed using the same techniques as baseline.

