- e) The corticosteroid dose at the time of the scan evaluation should be no greater than the dose at time of baseline scan.
- f) Stable or improved non-enhancing (T2/FLAIR) lesions on same or lower dose of corticosteroids compared to baseline scan.
- g) Stable or improved clinically.

**Note:** Subjects with non-measurable disease cannot have a partial response. The best response possible is stable disease.

Stable Disease (requires all of the following):

- a) Does not qualify for CR, PR, or progression.
- b) The designation of stable disease requires a minimum of 4-week duration.
- c) All measurable and non-measurable sites must be assessed using the same techniques as baseline.
- d) Stable non-enhancing (T2/FLAIR) lesions on same or lower dose of corticosteroids compared to baseline scan. In the event that the corticosteroid dose was increased for new symptoms and signs without confirmation of disease progression on neuroimaging, and subsequent follow-up imaging shows that this increase in corticosteroids was required because of disease progression, the last scan considered to show stable disease will be the scan obtained when the corticosteroid dose was equivalent to the baseline dose.
- e) Stable clinically.

Progressive Disease (defined by any of the following):

- a)  $\geq 25\%$  increase in sum of the products of perpendicular diameters of enhancing lesions compared to the smallest tumor measurement obtained either at baseline (if no decrease) or best response, on stable or increasing doses of corticosteroids.\*
- b) Significant increase in T2/FLAIR non-enhancing lesion on stable or increasing doses of corticosteroids compared to baseline scan or best response following initiation of

therapy,\* not due to co-morbid events (radiation therapy, demyelination, ischemic injury, infection, seizures, postoperative changes, or other treatment effects).

- c) Any new lesion.
- d) Clear clinical deterioration not attributable to other causes apart from the tumor (e.g., seizures, medication adverse effects, complications of therapy, cerebrovascular events, infection, etc.) or changes in corticosteroid dose. The definition of clinical deterioration is left to the discretion of the treating physician, but it is recommended that a decrease in 20% of KPS or from any baseline to 50% or less be considered, unless attributable to comorbid events.
- e) Failure to return for evaluation due to death or deteriorating condition.

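### Arm 1 entry uses a looser definition of measurable disease than response scoring does, so an eligible patient may be unable to count as a responder

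*Combined protocol and SAP*

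**What the plan says.** **Entry.** Section 3.2 item 3 reads: "Arm 1 patients must have measurable (defined by at least 1 cm x 1 cm) contrast-enhancing disease by MRI imaging". The scan may be no more than 21 days old when treatment starts. The definition is complete in itself. It says nothing about margins or slices and does not point to Section 8.1, although item 7 of the same list does cross-refer to another section.

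**Response scoring.** Section 8.1 requires "contrast-enhancing, measurable lesions with clearly defined margins by MRI scan, with a minimal diameter of 1 cm", and the lesion must also be "visible on 2 axial slices which are at least 5 mm apart with 0 mm skip".

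**Consequence of failing Section 8.1.** The note under complete response says: "Subjects with non-measurable disease cannot have a complete response. The best response possible is stable disease". The note under partial response says: "Subjects with non-measurable disease cannot have a partial response. The best response possible is stable disease".

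**Use in the design.** Section 11.0 makes objective response (PR+CR) the Arm 1 primary endpoint. Arm 1 stops if 2 or fewer of the first 19 patients respond, and succeeds if at least 7 of 31 evaluable patients respond. The protocol does not say what makes a patient evaluable for response. Section 9.2 states only who is evaluated for toxicity.

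**The concern.** A measurable-disease criterion belongs in a response-rate trial so that everyone enrolled can, in principle, be scored as a responder. Here the entry screen and the scoring rule use the same word with different content. Take a patient whose only enhancing lesion is 1.2 x 1.1 cm with ill-defined margins. That patient passes item 3, is properly registered and treated, and under Section 8.1 can do no better than stable disease whatever the drugs achieve.

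If such a patient is counted, the result is a fixed non-response. That makes both Arm 1 thresholds harder to reach for a regimen that works. Because Arm 2 opens only if Arm 1 meets its efficacy criteria, a false negative in Arm 1 would close Arm 2 as well.

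**Working it through.** **1. The two definitions side by side.**

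| Condition | Section 3.2 item 3 (entry) | Section 8.1 (scoring) |
|---|---|---|
| Contrast enhancement | required | required |
| Size | at least 1 cm x 1 cm | bidimensional, minimal diameter 1 cm |
| Clearly defined margins | not mentioned | required |
| Two axial slices at least 5 mm apart | not mentioned | required |

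The size threshold is the same. The gap is the last two rows.

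**2. Reproduce the plan's Arm 1 figures.** The inputs, all from Section 11.0, are n1 = 19 and n2 = 31 − 19 = 12; continue with 3 or more responses; succeed with 7 or more in total; rates 13% and 30%.

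P(success) = Σ over x = 3 to 19 of P(X1 = x) × P(X2 ≥ 7 − x), with X1 ~ Bin(19, p) and X2 ~ Bin(12, p). P(early stop) = P(X1 ≤ 2).

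- At p = 0.30: P(success) = 0.854 and P(early stop) = 0.046. The plan says power of at least 85%.
- At p = 0.13: P(success) = 0.095, so P(negative) = 0.905, and P(early stop) = 0.543. The plan says at least .90 and at least .54.

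All the stated figures are confirmed. Power exceeds 85% by less than half a percentage point.

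**3. Sensitivity to unscorable patients.** This step rests on three assumptions that the documents do not supply:
- k of the 31 patients have no lesion measurable under Section 8.1.
- They stay in the denominator, spread at random over the two stages.
- Scorable patients respond at rate p.

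With j of the k patients in stage 1, the scorable numbers are 19 − j and 12 − (k − j). The formula in step 2 is applied to those numbers and weighted by C(19, j) × C(12, k − j) / C(31, k).

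For k = 1 and p = 0.30, the patient falls in stage 1 with weight 19/31 (success probability 0.8263) or in stage 2 with weight 12/31 (0.8322). This gives 0.613 × 0.8263 + 0.387 × 0.8322 = 0.829.

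| k (assumed) | Power, 30% among scorable | Early stop at 30% | P(success), 13% among scorable |
|---|---|---|---|
| 0 | 0.854 | 0.046 | 0.095 |
| 1 | 0.829 | 0.055 | 0.082 |
| 2 | 0.799 | 0.064 | 0.071 |
| 3 | 0.766 | 0.076 | 0.060 |

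**4. Cross-check by diluting the rate.** Multiplying 30% by 30/31, 29/31 and 28/31 gives 29.0%, 28.1% and 27.1%. The step 2 formula then gives 0.827, 0.796 and 0.761, in close agreement with the table.

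**The case against.** **The denominator is not settled.** Section 11.0 bases the final rule on evaluable patients, and Section 8.1 opens by applying the RANO criteria to subjects with measurable disease. A patient with no such lesion could be treated as non-evaluable and replaced, with no loss of power. That reading is possible. So is the other: the notes in Section 8.1 give these patients a best response of stable disease, and the stage 1 rule refers simply to the first 19 patients. The objection stands to this extent: the power loss is conditional.

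**The stated power is not wrong.** A reader might infer that the design falls short of its 85%. It does not. At a true 30% rate among all patients counted, power is 0.854. The lower figures apply only if 30% is the rate among scorable patients and the unscorable ones are counted too.

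**The group is narrow.** The patient must have no other lesion that meets Section 8.1. A roughly round 1 cm lesion spans about 10 mm and can appear on slices 5 mm apart, so failing the slice condition needs a flattened lesion. Ill-defined margins are the more credible route. The documents give no frequency for either.

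**Two stronger readings do not hold.** A reader might infer a conflict in the opposite direction from Section 8.1's cavity-rim clause: "Measurement of tumor around a cyst or surgical cavity, if necessary, requires a minimum thickness of 3 mm". That clause sets a minimum for taking a measurement. It does not say that a rim is exempt from the 1 cm diameter or offer another route to measurability. A reader might also infer that sites will credit responses on unmeasurable lesions without challenge. Sections 8.2 and 8.4 limit that risk, because a neuroradiologist centrally reviews the scans of patients showing response and assesses tumor size independently.

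**Existing checks do not close the gap.** Section 7.0 has sites verify the eligibility criteria, and Section 8.4 has the ABTC Central Office review baseline documents. As written, the criterion being verified is item 3. The registration forms are not in the documents, so a stricter item on them cannot be excluded. Central imaging review covers patients showing response and is not an entry check.

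**Conclusion.** The inconsistency is real. Following the text as written, Arm 1 can enroll a patient whom Section 8.1 bars from the primary endpoint. This is a conflict between two stated rules and not an error in the sample-size calculation.

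Its likely effect is modest. With 1, 2 or 3 such patients retained among the 31, power against 30% in scorable patients is about 0.83, 0.80 or 0.77, against 0.854 with none. This depends on an assumed count and on an undefined denominator. The bias is toward a negative result: the chance of success at 13% falls from 0.095 to 0.082, 0.071 or 0.060, so this route gives no false-positive concern. The alignment should be made because it is cheap and the design has almost no power to spare above 85%.

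**What to change.** 1. In Section 3.2 item 3, replace the parenthetical size definition with a reference to measurable disease as defined in Section 8.1.
2. At registration, confirm that definition on the baseline MRI, which Section 4.2 already requires within 21 days before treatment.
3. In Section 11.0, state that evaluable for Arm 1 response means having baseline disease measurable under Section 8.1. The denominator then depends on a baseline fact and not on later judgement.

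The cost is a sentence in each of two sections and one line on the registration form. No extra scans are needed and the stated operating characteristics are unchanged. The downside is that a few borderline patients will be screened out, though under Section 8.1 they could not have contributed a response.

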### **3.3 Ineligibility Criteria**

[figure not shown]
1. Patients receiving any other investigational agents are ineligible.
2. Patient must not have known sensitivity to TRC102 or any formulation excipients.
3. Patients on enzyme-inducing anti-epileptic drugs (EIAED) are not eligible for treatment on this protocol. Patients may be on non-enzyme inducing anti-epileptic drugs or not be taking any anti-epileptic drugs. Patients previously treated with EIAED may be enrolled if they have been off the EIAED for 10 days or more prior to the first dose of TRC102.
4. Patients must not be on any anticoagulation.
5. Patient must not have prior gastrointestinal (GI) surgery or GI disease that might interfere with the absorption of TRC102.
6. Patients who have not recovered to <CTCAE grade 2 toxicities related to prior therapy are ineligible.
7. Patients must not have active brain metastases from a systemic solid tumor.
8. Patients with uncontrolled intercurrent illness including, but not limited to, ongoing or active infection, symptomatic congestive heart failure, clinically significant cardiac disease, unstable angina pectoris, cardiac arrhythmia, or psychiatric illness/social situations that would limit compliance with study requirements, are ineligible.

9. Pregnant women are excluded from this study because TRC102 has potential for teratogenic or abortifacients effects. Because there is an unknown but potential risk for adverse events in nursing infants secondary to treatment of the mother with TRC102, breastfeeding should be discontinued if the mother is treated with TRC102.
10. HIV-positive patients on combination antiretroviral therapy are ineligible because of the potential for pharmacokinetic interactions with TRC102. In addition, these patients are at increased risk of lethal infections when treated with marrow-suppressive therapy.

## 4.0 TREATMENT PLAN

This is a Phase II, open-label, multicenter study of TRC102 in patients with recurrent glioblastoma. All subjects must have had histological confirmation of glioblastoma by either biopsy or resection that is progressive or recurrent following radiation therapy + temozolomide.

This phase II trial will be performed in 2 sequential arms: the first arm of bevacizumab-naïve patients and the second arm of bevacizumab-failure patients.

\* *Arm 2 (bevacizumab refractory cohort) will only activate if Arm 1 (bevacizumab-naïve cohort) meets the statistical criteria of efficacy.* See Section [11.0](#), Statistical Considerations.

### 4.1 Treatment Schema

#### Arm 1: Bevacizumab-naïve patients

[figure not shown]
Arm 1 will estimate the efficacy of TRC102 and temozolomide (TMZ), as measured by response rate, in bevacizumab-naïve glioblastoma (patients may not have received prior treatment with bevacizumab).

#### Arm 2: bevacizumab-refractory patients

*(This arm will only activate if Arm 1 meets the statistical criteria of efficacy as defined in Section [11.0](#))*

Arm 2 will estimate the efficacy of TRC102 and TMZ, as measured by response rate, in bevacizumab-refractory glioblastoma (patients must have progressed/recurred following prior treatment with bevacizumab but should continue receiving bevacizumab as clinically indicated).

All patients will receive the maximum tolerated dose of oral TRC102 as determined in the NCI phase I trial, 150mg flat dose, combined with temozolomide 150mg/m^2 on days 1-5 every 28 days. The dose of temozolomide will remain at 150 mg/m^2 throughout the study.

TRC102 and TMZ are being given together as a combined treatment. If for any reason a patient is permanently taken off TRC102 or TMZ the patient will be off treatment.

An MRI will be performed prior to every odd-numbered cycle (every 8 weeks).

Patients will continue receiving TRC102 and TMZ until they meet the criteria for disease progression or other criteria for going off treatment (Section [10.0](#)). All patients will be followed for survival.

#### **4.2 Treatment Requirements**

All eligible patients who consent to this study must have a baseline (post-operative, if surgery is applicable) pre-treatment MRI. This baseline scan must be done within 21 days prior to the initiation of treatment.

Prior to every cycle patients must have:

- 1) ANC  $\geq$  1500/ $\mu$ l and platelets  $\geq$  100,000 / $\mu$ l.  
**AND**
- 2) All toxicities recovered to  $\leq$  grade 1 [or tolerable grade 2 for non-hematologic toxicity] or  $\leq$  baseline.

#### **4.3 Drug Administration**

No investigational or commercial agents or therapies other than those described below may be administered with the intent to treat the patient's malignancy.

Treatment will be administered on an outpatient basis. Patients will be provided with medication diaries and instructed in their use. Patients will be instructed to bring all unused medication and their diaries to each study visit for assessment of compliance.

##### **4.3.1 TRC102 Administration**

TRC102 will be administered on an outpatient basis once daily as an oral dose of 150mg flat dose given for 5 consecutive days every 4 weeks. Patients should take the dose approximately the same time each day, in the morning, at the same time as the temozolomide dose.

Drug should be taken on an empty stomach, 1 hour before a meal or 2 hours after a meal. Take with 8 ounces of water. Capsules should be swallowed whole, do not chew or crush.

If a patient misses or vomits a dose, he or she should be instructed not to take or make up that dose and to resume dosing with the next scheduled dose. Missed or vomited doses should not be made up. A dose will be considered missed, and should not be made up, if more than 6 hours have passed from the time the dose is normally taken.

#### 4.3.2 Temozolomide Administration

Temozolomide will be administered orally once a day for 5 consecutive days and repeated every 28 days. The dose will be 150 mg/m^2/day.

The dose administered will be determined using the body surface area (BSA) calculated at the beginning of each cycle. The BSA will be calculated from the height obtained at the baseline evaluation and from the weight obtained at the most recent pre-odd-numbered cycle evaluation before each 5-day TMZ treatment. Prior to each 5-day treatment with temozolomide a complete blood count (CBC) has to be obtained (within -5 days prior to dosing). The start of all 5-day TMZ treatments will be scheduled every 4 weeks (28 days, +3 days) after the first daily dose of temozolomide of the preceding 5-day treatment.

If liver function tests (alkaline phosphatase, total bilirubin, SGOT, SGPT) are abnormal, the decision to initiate temozolomide treatment should carefully consider the benefits and risks for the individual patient. For patients with significant liver function abnormalities, the benefits and risks of continuing treatment should be carefully considered.

Blood counts will be evaluated weekly. Within -5 days prior to the first dose of each 5-day TMZ treatment, the patient must have an ANC  $\geq$  1500/uL and platelet count  $\geq$  100,000/uL. On Day 1 of each cycle (within -5 days) all **non-hematological** toxicity grades 3 or 4 (except for alopecia, nausea and vomiting), related at least possibly to TMZ must have resolved (CTCAE grade  $\leq$  1 [or tolerable grade 2]). If toxicity persists, treatment should be delayed by one week for up to 3 consecutive weeks and directions for dose reduction should be followed (see Section [5.2](#)). If after 3 weeks of delay all toxicity has still not resolved then any further adjuvant treatment with temozolomide should be stopped (patient is off treatment).

For this study of the combination treatment of temozolomide and TRC102, the dose of temozolomide will remain at 150mg/m^2 for the duration of the study and not escalate to 200 mg/m^2. If during the first cycle the patient experiences **platelets < 50,000/uL and/or**

**ANC < 1000/ $\mu$ l and/or a non-hematologic toxicity  $\geq$  grade 3 then patient should follow directions for dose reduction in Section [5.2](#).**

Capsules of temozolomide are available in 5, 20, 100, 140, 180, 250 mg strengths. The daily dose will be rounded to the nearest 10 mg. The exact dose administered should be recorded in the CRF. Each daily dose should be given with the least number of capsules.

Temozolomide should be taken at the same time as TRC102 capsules on an empty stomach, 1 hour before a meal or 2 hours after a meal. Take with 8 ounces of water. Patients should be told to swallow the whole capsules in rapid succession without chewing them. If vomiting occurs during the course of treatment, no re-dosing of the patient is allowed before the next scheduled dose. Missed doses should not be made up. A dose will be considered missed, and should not be made up, if more than 6 hours have passed from the time the dose is normally taken.

